11.3. Appendix 3: Data Display Standards & Handling Conventions

11.3.1. Study Treatment & Sub-group Display Descriptors

Treatment Group Descriptions			
RandAll NG		Data Displays for Reporting	
Code	Description	Description	Order ^[1]
A	GSK2646264 X.X mg	GSKX.X mg	2
P	Placebo	Placebo	1

NOTES:

1. Order represents treatments being presented in TFL. Placebo is to be presented at start in Tables, Figures and Listings. Dosing of GSK treatment will be displayed in ascending order, where appropriate.

In accordance with the body surface area (BSA) to be used Arm, Leg and Front Torso of the subjects had to be treated on the different body sides with either GSK2646264 or matching placebo treatment as displayed below:

Table 11 Overview of Treatments Doses and Analyses.

Part	Dose	BSA treated per body side (left/right)	Day of Treatment (Tests performed)	Comment
A	0.5% (Group 1)	0.2% 1% 5%	D1 (PK/PD) D2 (PK) D3 (PK/PD)	qd
A	1.0% (Group 2)	5% 5% 10% 10%	D1 (PK/PD) D2 (PK) D3 (PK/PD) D4 (PK)	qd
B	.0.5 or 1%	0.2%+5% 0.2%+5% 0.2%+5%	D1(PK/PD) D2 D3(PK/PD)	qd or bid (D3 morning dose only)
C	.0.5 or 1%	X.X2%	D1 (PK/PD) D2 (PD) D3 (PD) D4 (PK/PD) D5 (PD) D6 (PD) D7 (PK/PD)	Qd or bid

¹ maximum tolerated dose (taken from Part A)

² maximum BSA treated (taken from Part A)

The following changes to treatment dosing were made to dose group 2 (Part A) in light of dose escalation review meeting at the end of dose group 1:

Table 12 Treatment applied to specified areas per day on Part A; healthy subjects, n=9, dose group 2

	Day 1-2	Day 3-4	Day 5 to 7
Area	AM ^a	AM ^a	
Left Arm	0.36g of 1.0% ^b GSK2646264 or placebo cream applied to 36cm ² (~0.2% BSA)		NO DOSING
Right Arm	0.36g of 1.0% ^b GSK2646264 or placebo cream applied to 36cm ² (~0.2% BSA)		NO DOSING
Left Front Torso	9g of 1.0% ^b GSK2646264 or placebo cream applied to 900cm ² (~5% BSA)	18g of 1.0% ^b GSK2646264 or placebo applied to 1800cm ² (~10% BSA)	NO DOSING
Right Front Torso	9g of 1.0% ^b GSK2646264 or placebo applied to 900cm ² (~5% BSA)	18g of 1.0% ^b GSK2646264 or placebo applied to 1800cm ² (~10% BSA)	NO DOSING

a. AM dosing only

b. 0.5% strength may be used if data for Part A and/or group 2 supports

11.3.2. Baseline Definition & Derivations

11.3.2.1. Baseline Definitions

For all endpoints (expect as noted in baseline definitions) the baseline value will be the latest pre-dose assessment.

Parameter	Study Assessments Considered As Baseline			Baseline Used in Data Display
	Screening	Day -1	Day 1 (Pre-Dose)	
Safety Assessment				
Laboratory	X	X ²		Day -1, (Part A & B) Screening (Part C)
Vital Signs	X		X	Day 1 (pre)
ECG	X	X		Screening ¹
Pharmacodynamics				
Allergen Challenge SPT (Part A & B)				No baseline
Cold Temp test (Part B)				No baseline
UAST (Part C)	X			Screening
AAS (Part C)	X			Screening

Parameter	Study Assessments Considered As Baseline			Baseline Used in Data Display
	Screening	Day -1	Day 1 (Pre-Dose)	
Health Outcome				
DLQI (Part C)	X			Screening

NOTES :

1. Use the mean of replicate assessments at any given time point as the value for that time point in all summaries, figures and statistical analyses.
2. Not in Part C

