#### **4.2.1.4. Additional Inclusion criteria specific for subjects with chronic spontaneous urticaria (Part C)**

Subjects will be included in the chronic spontaneous urticaria cohort if all the following criteria apply

1. The subject is aged between 18 and 70 years of age inclusive, at the time of signing the informed consent.
2. Body weight  $\geq$  50 kg and BMI within the range 19 to 35 kg/m^2 (inclusive)
3. Subjects who have a score of  $>14$  on the UAS7 questionnaire with between 4-20 weals observed in a defined area of the body will be included in this study. This area must include either arms, legs or torso for 7 consecutive days during the screening period, prior to the Day 1 visit. If a subject has not completed 7 consecutive days of UAS questionnaire prior to dosing on Day 1 due to exceptional circumstances, the screening period may be extended until the subject has completed 7 consecutive days of UAS questionnaire. This will only be at the discretion of the Investigator.
4. No other aetiology identified for chronic urticaria such as drug-related or inducible urticaria as determined by history, physical examination and laboratory studies.
5. Subjects must be free from any past or present benign or malignant skin conditions and disease, other than the specified condition required for eligibility of subjects as defined in the specific inclusion criteria for CsU cohort unless in the opinion of the investigator it will not compromise the subjects safety and quality of data.

6. Other than a diagnosis of chronic spontaneous urticaria the subject should have no other co-morbidities which would introduce additional risk factors and will not interfere with the study procedures, as determined by a responsible and experienced physician, based on a medical evaluation including medical history, physical examination, laboratory tests and cardiac monitoring.
7. A subject with a clinical abnormality or laboratory parameter(s) which is/are not specifically listed in the inclusion or exclusion criteria, outside the reference range for the population being studied may be included only if the Investigator, in consultation with the GSK Medical monitor if required, agrees and documents that the finding is unlikely to introduce additional risk factors and will not interfere with the study procedures.

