### 6.1.4. Part C: Chronic Spontaneous Urticaria Cohort

Day:	Screening	1	2	3	4	5	6	7	8	Day 10 ( $\pm$ 1 day)	Day 15 ( $\pm$ 1 day)	Follow-up Day 22 ( $\pm$ 1 day)	Notes
Visit Window (relative to Day 1)	-28 to -7 												1. Screening can occur on any day between 28 days and 7 days prior to Day 1 dosing.
Informed Consent	X												
Demographics	X												
Complete physical	X											X	
Body weight (kg)	X												
Height (cm) without shoes	X												
Brief physical		X											
Medical/medication/drug/alcohol history	X												
12-lead ECG	X 	X						X				X	2. Triplicate ECG at screening and CV risk factors
Vital signs	X	X		X			X			X 	X 	X 	3. To be performed on same day as PK samples
Urine alcohol screen	X	X											
Pregnancy Test (Women of child bearing potential) 	X(S) 	X (U) 						X(U) 		X (S)	X(S)		4. A serum (S) pregnancy test will be performed on the day of screening. If the day of screening is between Days -13 and -7, a further pregnancy test will not be required until Day 1. However, if the day of screening is between Days -28 and -14, an additional serum pregnancy test will be required between Days -7 and -4.

Day:	Screening	1	2	3	4	5	6	7	8	Day 10 ( $\pm$ 1 day)	Day 15 ( $\pm$ 1 day)	Follow-up Day 22 ( $\pm$ 1 day)	Notes
													5. A urine pregnancy test is required prior to dosing on Day 1 & Day 7
HIV, Hep B and Hep C screen	X												
Clinical Laboratory Tests	X	X						X				X	
TSH, free T4, T4, T3	X							X		X6	X6	X6	6. Sample to be taken on same day as PK sample
Blood Sample for CD69 expression		X 		X 		X 			X 	X 	X 		7. Pre-dose 8. 4 hours post dose 9. Sample to be taken on same day as PK sample
Randomisation		X											
UAS-7 Diary	X 		X 	X					10. Screening UAS7 diary will be completed for the 7 successive days before Randomisation (Day 1). If there is a lapse in any day prior to Day 1 the subject must complete the full 7 days worth of diary entries again during the screening period. 11. The UAS-7 diary should be completed pre-dose on those days where dosing occurs				
QOL (DLQI)	X	X 							X				12. The baseline DLQI assessment on Day 1, looking back over the previous 7 days prior to dosing, should be completed pre-dose

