## **6.6. Health Outcomes**

### **6.6.1. Dermatology Life Quality Index**

For the chronic spontaneous urticaria subjects in Part C, the health outcome measure of Quality of Life will be captured at Screening, Baseline and Day 8, using a 10-item Dermatology Life Quality Index (DLQI) ([Finlay](#), 1994) questionnaire. An overall score will be calculated as well as the following domains: Symptoms and Feelings, Daily Activities, Leisure, Work and School, Personal Relationships, and Treatment. A detail of questionnaire is provided in [Appendix 4](#). The days on which to record the DLQI are captured in the T&E Table (Section 6.1.4). On days where dosing occurs (Day 1 only), it will be completed pre-dose.

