11.2.1.4. Part C (Chronic Spontaneous Urticaria Cohort)

Day:	Screening	1	2	3	4	5	6	7	Follow-up	Notes
Visit Window (relative to Day 1)	-28 to -7 days								9-14 days after last dose	
Informed Consent	X									
Demographics	X									
Complete physical	X							X		
Body weight (kg)	X									
Height (cm) without shoes	X									
Brief physical		X						X		
Medical/medication/drug/alcohol history	X									
12-lead ECG ¹	X	X					X	X		1. Triplicate ECG at screening and CV risk factors questionnaire
Vital signs	X	X		X		X		X		
Urine drug/alcohol screen	X	X								

Day:	Screening	1	2	3	4	5	6	7	Follow-up	Notes
Visit Window (relative to Day 1)	-28 to -7 days								9-14 days after last dose	
Pregnancy Test (women) ²	X(S)	X (S/U)							X(S)	2. Pregnancy test will be performed 3 times during screening, serum (S) on day -28, day -7 to -4, and a serum or urine (U) pregnancy test the day of the start of the study prior to dosing and a serum pregnancy test at the follow up visit
HIV, Hep B and Hep C screen	X									
Clinical Laboratory Tests	X	X					X	X		
TSH ³	X									3. TSH test only at screening only
Blood Sample for CD69 expression ¹¹		X ⁹						X ¹⁰		9. Predose 10. 4 hours post dose 11 A decision will be made after Part A on whether samples are taken in Part C
Randomisation	X									
UAS-7 Diary ⁴	X	X	X	X	X	X	X	X		4. Screening UAS7 diary will be completed using 7 successive days before randomisation (day 1). If there is a lapse in any day prior to day 1 the subject must complete the full 7 days worth of diary entries again during the screening period.
QOL (DLQI)	X	X						X		
AAS	X	X	X	X	X	X	X	X		
AE assessment		X ⁸ ←-----→						X		8. Tolerability assessment at pre – and post-dose

CONFIDENTIAL

200196

Day:	Screening	1	2	3	4	5	6	7	Follow-up	Notes
Visit Window (relative to Day 1)	-28 to -7 days								9-14 days after last dose	
BHR- Basophil Histamine Release Test		X ⁵								5. Sample taken predose
Pharmacokinetic Blood Sample ⁶		X			X			X		6. PK blood sample taken at pre-dose sample and 2 and 4hr post dose
Study Treatment Dosing		X	X ⁷	X ⁷	X	X ⁷	X ⁷	X		7. The nurse will visit the subject at home to apply the dose
Outpatient visit	X	X			X			X	X	

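### The SAP takes the Part C DLQI baseline from Screening where the protocol names the Day 1 pre-dose assessment; the Part C laboratory baseline needs its Day 1 sample time settled

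*SAP*

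**What the plan says.** **SAP.** Section 11.3.2.1 gives a general rule and a table. The rule opens "For all endpoints (expect as noted in baseline definitions" and goes on to say that "the baseline value will be the latest pre-dose assessment". In the table, the Part C laboratory entry is "Screening (Part C", and the DLQI row marks only the Screening column. The Part C schedule in SAP 11.2.1.4 collects DLQI at Screening, Day 1 and Day 7. Its row "Clinical Laboratory Tests" is marked at Screening, Day 1 and later visits, with no note on the time of the Day 1 sample. SAP 9.1.3.1 analyses DLQI change by paired t test, and the programming note for Table 5.14 says that no treatment comparison is involved. The SAP synopsis ties the plan to protocol Amendment 2.

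**Protocol (Amendment 5).** Note 12 to the Part C schedule in 6.1.4 reads "The baseline DLQI assessment on Day 1, looking back over the previous 7 days prior to dosing, should be completed pre-dose". Section 6.6.1 says that quality of life "will be captured at Screening, Baseline and Day 8", so Screening and Baseline are separate time points. On the window, 6.1.4 says "Screening can occur on any day between 28 days and 7 days prior to Day 1 dosing", and inclusion criterion 3 in 4.2.1.4 adds that, in exceptional circumstances, "the screening period may be extended until the subject has completed 7 consecutive days of UAS questionnaire". The protocol defines no laboratory baseline. Section 6.3.4 requires fasting glucose at screening only.

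**The concern.** A change score should start as close to the first dose as the schedule allows. Here a later DLQI is scheduled, the protocol calls it the baseline, and the SAP table gives it no role. Chronic spontaneous urticaria fluctuates, and the DLQI describes a week already past, so a Screening value can describe a state that had passed before treatment began.

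The DLQI analysis is where this bites. A within-subject test has no placebo contrast to absorb movement before dosing. Improvement or worsening between Screening and Day 1 would be reported as change from baseline and could be read as a response to the cream.

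Laboratory tests are part of the primary safety endpoint. Change summaries, and the three change-based flags in SAP 11.6.1 (haematocrit fall 0.075, haemoglobin fall 25 g/L, creatinine rise 44 µmol/L), depend on which sample is the baseline.

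**Working it through.** No plan figure depends on the baseline choice, so there is none to reproduce. The check is day arithmetic, a decomposition and a comparison of sections.

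**1. Age of the baseline.** SAP 11.4.1 counts study days without a Day 0, so Screening on Day −s is s days before Day 1. With s from 7 to 28, the lag is 7 to 28 days, and more if screening is extended.

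**2. Week described.** Assume that the Screening DLQI is completed on the Screening day and has the same 7-day look-back that the protocol states for Day 1.

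| DLQI completed | Days described |
|---|---|
| Day −28 | −35 to −29 |
| Day −7 | −14 to −8 |
| Day 1, pre-dose | −7 to −1 |

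The Screening look-back ends on Day −(s + 1), which is Day −8 at the latest. It therefore never overlaps the week before dosing. The UAS7 and AAS baselines are diaries kept on the 7 successive days before Day 1 (protocol 6.1.4, notes 10 and 13), the same week that the Day 1 DLQI describes.

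**3. Share of the interval before dosing.** Day 1 to Day 8 is 7 days. From Screening the interval is 7 + 7 = 14 days up to 28 + 7 = 35 days. The part before dosing is 7/14 = 50% up to 28/35 = 80%.

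**4. What the paired test estimates.**

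Day 8 − Screening = (Day 8 − Day 1) + (Day 1 − Screening)

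The mean of the second term enters the reported change in full. The documents give no DLQI standard deviation, correlation or drift, so its size can only be scaled. Assume equal SDs, correlation r between the baseline used and the Day 8 score, and the 12 active subjects that 3:1 allocation of 16 implies. The 95% half-width of the mean change is t(0.975, 11) × √(2(1 − r)) / √12, in SD units:

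| r | 0.9 | 0.8 | 0.7 | 0.5 |
|---|---|---|---|---|
| Half-width (SD) | 0.28 | 0.40 | 0.49 | 0.64 |

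With no true change after dosing, an expected drift of this size puts the expected estimate one half-width away from zero.

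**5. The protocol's own model.** Protocol 9.3.2.4.1 specifies ANCOVA with treatment, baseline and location. Under randomisation, expected drift is the same in both arms and cancels from the treatment difference; a more distant baseline costs precision. For 12 against 4, leaving location out, the half-width is about t(0.975, 13) × √(1 − r²) × √(1/12 + 1/4): 0.54, 0.75, 0.89 and 1.08 SD for the same four values of r.

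**6. Laboratory tests.** Parts A and B use Day −1 as baseline, with Screening only as a fallback (SAP 11.3.2.2). The footnote to the laboratory row explains that Part C has no Day −1 visit but does not mention the Day 1 sample, which both schedules contain. In protocol 6.1.4 the Day 1 CD69, BHR, DLQI and urine pregnancy assessments are marked pre-dose, and PK is marked pre-dose and 4 hours post-dose. Clinical laboratory tests carry no mark. Fasting is required before the Screening visit (protocol 4.3.2.2) and for glucose only then (6.3.4), so the glucose change in SAP Table 3.9 would compare a fasting value with values not required to be fasting.

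**The case against.** A reader might infer that the SAP breaks its own latest-pre-dose rule. It does not. The rule exempts whatever the baseline definitions note ('expect' is evidently a misprint for 'except'), and the table beneath it is where the Screening entries are noted. The fair criticism is that the exceptions carry no adequate reason.

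A reader might also infer that the laboratory baseline contradicts the protocol. The protocol sets none, and the Day 1 sample is a later pre-dose value only if it is drawn before dosing, which neither document states. Most laboratory flags, including those for glucose, are absolute limits that do not use a baseline.

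Version history explains the DLQI conflict. The explicit Day 1 pre-dose wording, and the separate listing of Screening and Baseline, came with Amendment 4, and the SAP is written to Amendment 2. This is a plan left unaligned, not a departure from text its authors had. The limit on fasting glucose also dates from Amendment 4. Even so, the SAP's own schedule already held a Day 1 DLQI, so a later assessment was available and passed over.

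Finally, DLQI is exploratory, no hypothesis is formally tested, and under the protocol's ANCOVA the treatment difference is not expected to be biased. All of that stands. It does not rescue the paired analysis that the SAP specifies. SAP 9.1.3.1 does promise an estimated treatment difference, but neither the stated test nor Table 5.14 supplies one.

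**Conclusion.** The DLQI point holds. The SAP baseline is 7 to 28 days older than the one the protocol names, never describes the week before dosing, and leaves 50% to 80% of the Screening-to-Day 8 interval before the first dose. With the SAP's paired t test, drift over that time counts one for one as change. This affects every Part C DLQI change score: 16 planned subjects in the current protocol, 12 in the SAP. The amount of drift is unknown, and the look-back comparison assumes the same 7-day recall at Screening.

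The laboratory point holds only conditionally: an unexplained exception that should give way to Day 1 if that sample is drawn before dosing. The glucose mismatch follows from the documents as they stand.

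Two limits apply. UAS7 and AAS are not affected, because the protocol itself takes their baseline from screening (9.3.2.3.2) and the diaries fall in the week before Day 1. Nor does a Day 1 baseline turn a within-subject change into a controlled comparison. Subjects must exceed a UAS7 of 14 over a pre-dose week, so regression to the mean can remain.

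**What to change.** 1. In the SAP 11.3.2.1 table, change the Part C DLQI row to Day 1 pre-dose, with Screening used only if Day 1 is missing.
2. State whether the Part C Day 1 laboratory sample is drawn before dosing. If it is, make it the Part C laboratory baseline with Screening as fallback. If it is not, keep Screening, give the reason, and footnote that Screening glucose is fasting.
3. Extend the fallback sentence in SAP 11.3.2.2, which now covers only a missing Day −1 value, to a missing Day 1 value.

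The cost is one table row, one conditional row, a sentence on sample time and a sentence on fallback, with matching footnotes on the DLQI and laboratory change outputs. Day 1 DLQI and Day 1 laboratory tests are already in both schedules, so no visit or sample is added.

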11.3.2.2. Derivations and Handling of Missing Baseline Data

Definition	Reporting Details
Change from Baseline	= Post-Dose Visit Value – Baseline
% Change from Baseline	= $100 \times [(Post-Dose Visit Value - Baseline) / Baseline]$
% inhibition	= $[(control - treatment)/control] \times 100$

NOTES :

- Unless otherwise specified, the baseline definitions specified in Section 11.3.2.1 Baseline Definitions will be used for derivations for endpoints / parameters and indicated on summaries and listings.
- Unless otherwise stated, if baseline data is missing no derivation will be performed and will be set to missing.
- As only one baseline will be defined for all parameters (i.e. at the start of the study), there will only be one baseline on all summaries (i.e. not a separate baseline for each subsequent repeat dose).
- The baseline definition will be footnoted on all change from baseline outputs, where applicable.
- If baseline value for (day -1) is missing, screening value will be used as baseline. If both assessments are missing then no derivation will be performed and will be set to missing..

11.3.3. Reporting Process & Standards

Reporting Process	
Software	

 • The currently supported versions of SAS software will be used to perform all data analyses and generation of displays (tables, figures, and listings). 	
Reporting Area	
HARP Server	PHU058
HARP Area	: \ARWORK\GSK2646264\final or \ARWORK\GSK2646264\final
QC Spreadsheet	: Not applicable]
Analysis Datasets	

 • Analysis datasets will be created according to CDISC / ADaM Standards Library standards. For creation of ADaM datasets (ADCM/ADAE), the same version of dictionary datasets will be implemented for conversion from SI to SDTM. 	
Generation of Files	

 • PDF files will be generated. 	

Reporting Standards	
General	

 The current GSK Integrated Data Standards Library (IDSL) will be applied for reporting, unless otherwise stated: 
 o 4.03 to 4.23: General Principles o 5.01 to 5.08: Principles Related to Data Listings o 6.01 to 6.11: Principles Related to Summary Tables o 7.01 to 7.13: Principles Related to Graphics 	
Formats	

 All data will be reported according to the actual treatment the subject received unless otherwise stated. GSK IDSL Statistical Principles (5.03 & 6.06.3) for decimal places (DP's) will be adopted for reporting of data based on the raw data collected. Numeric data will be reported at the precision collected on the eCRF. The reported precision from non eCRF sources will follow the IDSL statistical principles but may be adjusted to a clinically interpretable number of DP's. 	
Planned and Actual Time	

 Reporting for tables, figures and formal statistical analyses : 
 Planned time relative to dosing will be used in figures, summaries, statistical analyses and calculation of any derived parameters, unless otherwise stated. The impact of any major deviation from the planned assessment times and/or scheduled visit days on the analyses and interpretation of the results will be assessed as appropriate. Reporting for Data Listings: 
 Planned and actual time relative to study drug dosing will be shown in listings (Refer to IDSL Statistical Principle 5.05.1). Unscheduled or unplanned readings will be presented within the subject's listings. Visits outside the protocol defined time-windows (i.e. recorded as protocol deviations) will be included in listings but omitted from figures, summaries and statistical analyses. 	
Unscheduled Visits	

 Unscheduled visits will not be included in summary tables. Unscheduled visits will not be included in figures. All unscheduled visits will be included in listings. 	
Descriptive Summary Statistics	
Continuous Data	
Refer to IDSL Statistical Principle 6.06.1
 
➤ N, n, mean, 95% CI of the mean, standard deviation (SD), median, minimum (min) and maximum (max).

Categorical Data	N, n, frequency, %
Reporting of Pharmacokinetic Concentration Data	
Descriptive Summary Statistics	
Refer to IDSL Statistical Principle 6.06.1
 
Assign zero to NQ values (Refer to GUI_51487 for further details)

Reporting of Pharmacokinetic Parameters	
Descriptive Summary Statistics	N, n, geometric mean, 95% CI of geometric mean, standard deviation (SD) of logged data and [between and or within] geometric coefficient of variation

Reporting Standards	
(Log Transformed)	(CV _{b/w} (%)) will be reported. [1] CV _b (%) = $\sqrt{(\exp(\text{SD}^2) - 1) * 100}$ (SD = SD of log transformed data) [2] CV _w (%) = $\sqrt{(\exp(\text{MSE}) - 1) * 100}$ (MSE = mean square error from mixed effect model of loge-transformed data).
Graphical Displays	

Refer to IDSL Statistical Principals 7.01 to 7.13.	

